HUMAN SUBJECTS RESEARCH PROTOCOL

1. PROTOCOL TITLE: Safety, feasibility, and benefits of transcranial direct current stimulation (tDCS) in human subjects with PTSD receiving an exposure-based, behavioral therapy

2. ABSTRACT.

1 2 3

4 5 6

7

8 9

26

Symptoms of posttraumatic stress disorder (PTSD) include intrusive memories about the event, physiological hyperarousal, 10 11 sleep difficulties, and negative alterations to mood and cognitions, all of which can have significant, long-term effects on 12 health and functioning. Evidence-based non-pharmacological, psychotherapies for PTSD exist and are well-established (Lewis et al., 2020). However, there remains room for improvement in outcomes given that a proportion of patients (~50%) do 13 not significantly benefit from treatment (Steenkamp et al., 2015a). The field of non-invasive brain stimulation is rapidly gaining 14 considerable attention as a potential therapeutic for PTSD based on the ability to modulate brain activity in regions associated 15 with the fear response and extinction learning (two critical constructs associated with PTSD pathology and PTSD treatment). 16 While the potential for non-invasive brain stimulation is exciting, research is needed to determine the safety, feasibility, and 17 benefits of non-invasive brain stimulation in human subjects with PTSD. Towards this end, we will conduct a partially double -18 19 blind randomized controlled pilot study of transcranial direct current stimulation (tDCS) vs. a sham condition in a sample of 40 20 adults with PTSD receiving 5 weekly sessions of Written Exposure Therapy (WET), an exposure-based, behavioral 21 psychotherapy for PTSD. 22

23 3. OBJECTIVES/SPECIFIC AIMS/RESEARCH QUESTIONS.

The primary objective of this study is to evaluate the safety, feasibility, and psychological and physiological treatment 24 25 benefits of tDCS, a noninvasive brain stimulation technique, when delivered in combination with WET for PTSD.

27 Specific Aims and Hypotheses:

- Aim 1: To evaluate the safety of tDCS vs. sham when combined with WET. 28
- 29 Hypothesis 1: tDCS can be safely combined with WET for PTSD as indicated by minimal adverse events (AEs) and 30 high tolerability of any observed study related AEs.

Aim 2: To evaluate the feasibility of combining tDCS with WET for PTSD as measured by rates of enrollment, recruitment, 31 and treatment completion. 32

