Title: Safety, feasibility, and benefits of transcranial direct current stimulation (tDCS) in human subjects with PTSD receiving an exposure-based, behavioral therapy

169 Psychiatry Outpatient Clinics, and the San Antonio community. Participants will be recruited from the South Texas Veterans Healthcare System (SVTHCS) by responding to flyers approved and posted by Public Affairs. Interested 170 171 participants who appear to meet eligibility criteria will be consented and then complete a baseline assessment to 172 determine study eligibility. Eligible participants will be randomized to five weekly sessions of tDCS, or sham, combined 173 with WET for PTSD. tDCS (or sham) will be simultaneously delivered during the writing exposure portion of WET for 30 174 minutes each session. Outcomes to address study objectives will include (1) safety as measured by the adverse events (AE) monitoring logs, (2) feasibility based on study recruitment (number of contacted referrals who were eligible to begin 175 the full baseline assessment over the total number of contacted referrals [will not to include non-contact referrals]). 176 screening (number screened eligible following baseline assessment over the total number of individuals who completed a 177 baseline assessment), and treatment completion (number who completed all 5 sessions over total randomized), and (3) 178 the associated effects of tDCS for PTSD as measured by the PCL-5 and physiological stress response (as measured by 179 180 heart rate and galvanic skin response). Assessments will be collected twice to satisfy study aims at baseline and one-181 month follow-up. Select measures will also be administered during treatment (Table in section 7.3).

183 6.1.1. Randomization. This study will use a partially double-blind randomization design. All participants will be blinded to 184 treatment arm. With the exception of one non-clinical, research team member, all other members of the research team will also be blinded to treatment arm. This approach is so that the PI and research team can be quickly made aware of which 185 186 treatment arm the participant is assigned to in the event of an emergency.

188 7. RESEARCH PLAN.

182

187

189

195

197

198

199

201

202

203

204

205

206

207 208

209

210

211

212

213

214

215 216

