Only select STRONG STAR Data and Statistics Services personnel have direct access to the data on a "need to access basis"; for example (but not limited to) detecting and repairing data corruption and producing reports not currently within the STRONG STAR system. STRONG STAR Data and Statistics Services also follows the Principals of Least Privilege (POLP). All user activity is tracked and recorded within the system so if any records are added, altered, or viewed the action is recorded and can be recalled for auditing purposes. Access to this information will require a password-protected login available only to authorized STRONG STAR Data and Statistics Services staff.

Every member of the Research Team will be trained and monitored about how to handle and protect both research
records. Furthermore, the Research Team strictly controls access to study data. The STRONG STAR Data Safety and
Monitoring Plan (DSMP) that has been developed in accordance with the National Institutes of Health Office of Human
Research Protection to assure the appropriate clinical safety monitoring of study subjects participating in research will be
used to monitor this study.

377

378**7.4 Statistical Consideration**379

7.4.1 Sample Size Estimation.

381

382

389

Total Required to Consent	50
Estimated Participant Screen Fail / Exclusion (20%)	10
Target Sample Size to be Randomized	40
Estimated Participant Drop Out / Withdrawal after randomization (15%)	6
Expected Treatment Completers	34

7.4.2 Primary (i.e., primary outcome variables) and secondary endpoints (See Table in section 7.3). Adverse event
 (AE) monitoring will address study Aim 1. To assess study feasibility (Aim 2), we will track study recruitment (number of
 eligible referrals/total referrals), enrollment (number of screened enrolled participants/total eligible), and treatment
 (number of participants who completed all 5 WET sessions). The PCL-5 (Weathers, Litz, et al., 2013) will be the primary
 outcome to assess PTSD severity (Aim 3a). Heart rate (HR) and galvanic skin response (GSR) will be used to address
 Aim 3b.

390 **7.4.3 Data analysis.**

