408 409 Descriptive Statistics to Address Aims 1 and 2: Descriptive statistics will be used to address the safety and feasibility of 410 tDCS when combined with WET. To assess, safety, we will evaluate the frequency, severity, and relatedness of AE based on the STRONG STAR AE monitoring procedures. AE logs will be reviewed and adjudicated with the study team during 411 weekly meetings to evaluate reliable coding and participant safety. [name]. PsvD (PI) and [name] (Co-I: 412 Attending Physician) will also hold one-on-one meetings as needed to mitigate health related AEs and monitor 413 participants. To assess study feasibility, we will estimate recruitment (number of eligible referrals/total referrals). 414 enrollment (number of screened enrolled participants/total eligible), and treatment (number of participants who completed 415 416 all 5 WET sessions). Feasibility data will be used to inform planning for a larger clinical trial.

417

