485 486 tDCS: The most common adverse effect of tDCS include mild itching sensation at the point of contact with the electrodes. These AEs can be mitigated by excluding individuals with a history of skin condition, the use of saline solution, and 487 limiting the intervention to 40 min or less with ~1-week in-between sessions. 488 489

WET: Temporary increases in psychological distress can occur among individuals engaged in WET for PTSD. 490

492 Less Likely, some may be Serious (expected to occur in 10-18 out of 100 participants):

493 494 tDCS: Transient minor discomfort can occur in about 10-18% of participants, such as mild headaches, nausea, mild 495 burning sensation at the point of electrode contact, and fatigue. However, the relatedness of AEs to tDCS remains unclear 496 as many controlled trials have demonstrated no difference between the tDCS and sham conditions.

- 498 Rare and Serious (expected to occur in <1 out of 100 participants):
- 499 tDCS: A rare but serious AE of tDCS can be skin lesions following repeated tDCS. As noted above, the risk of both skin 500 lesions and itching/burning sensations can be minimized by soaking the connecting sponges in sodium chloride (saline) 501 solution rather than water before commencement of stimulation. Another potentially serious AE that has been discussed 502 503 in the literature is seizures. To date, there is no documented evidence that tDCS has resulted in a seizure and this may be explained by the subthreshold current used in tDCS. However, there is a theoretical rationale that brain stimulation can 504 505 increase the risk of seizures.
- 506 507 Risks to Confidentiality: With the handling of medical and research records there is always the possibility of a breach of 508 confidentiality. We will maintain patients' names, contact information (i.e., Identifiers), and all PHI (protected health information) in an encrypted computer database and all PHI identifiers will be removed in the database during data 509 510 analysis. Every member of the Research Team is carefully trained and monitored about how to store, handle, and protect 511 participant records.
- 513 Risks of PTSD Diagnosis regardless of Treatment: One of the risks of PTSD both in and out of treatment is attempted 514 suicide, which can result in death. Increased suicidality is possible during study participation. 515
 - 56GTSPH3C08UU94FUFQ8ULIG00.docx STRONG STAR Template Version 01/31/22

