537 The risk for the mild itching sensation at the point of contact with the electrodes will be mitigated by excluding individuals 538 with a history of skin condition, the use of saline solution, and limiting the intervention length to 30 min with ~1-week in-539 between sessions.

540

541 WET: Psychological distress experienced by participants is expected to be temporary and participants will be provided immediate coping tools and techniques to manage distressing emotions by the study therapist. Any indication that the 542 participant is considering suicide, endorses active psychosis/mania, or other harm to self/others will be handled using 543 evidence-based procedures and policies developed by the STRONG STAR Consortium. Participants who endorse 544 mania/psychotic symptoms will prompt a clinical interview with a licensed clinical provider to assess current risk and risk 545 of active mania/psychosis during study participation. Individuals with active mania/psychosis will be excluded from study 546 547 participation. Trained clinicians and evaluators will assess history of suicide and current suicidal ideation using the 548 Suicidal Ideation Thoughts and Behaviors Interview at the baseline assessment. Prior to each session individuals will also 549 complete self-report questionnaires to monitor PTSD, depression, and suicidality symptoms. Participants identified as low to moderate risk for suicide based on the assessment results may be maintained on the protocol and additional risk 550 management procedures will be implemented within the context of the study treatment. For participants identified as being 551 at high risk for suicide based on the assessment results, disenrollment will be considered if it is unlikely that standard 552 553 treatment plus additional risk management procedures will maintain safety. High risk participants who are disenrolled from 554 the study will be referred for more intensive treatment (outpatient or inpatient).

For urgent issues that occur in between appointments, whether related to tDCS or WET, participants will be instructed to get help immediately by going to the nearest emergency room. All participants will be given a study device emergency department wallet card at the beginning of the study. Participants will be instructed to keep this card on their person throughout the study. The wallet card briefly describes the study intervention (tDCS vs. sham) and provides a study team contact number.

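### Aim 1 plans no by-arm summary of suicidality: the DSI-SS is collected at all seven assessments, but safety is analysed through adverse events only

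*Combined protocol and SAP*

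**What the plan says.** Section 3 words Aim 1 as a comparison: "To evaluate the safety of tDCS vs. sham when combined with WET". Three places then say how it will be answered, and all three name adverse events:

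- Section 6: "Outcomes to address study objectives will include (1) safety as measured by the adverse events (AE) monitoring logs".
- Section 7.4.2: adverse event monitoring "will address study Aim 1".
- Section 7.4.3: "we will evaluate the frequency, severity, and relatedness of AE based on the STRONG STAR AE monitoring procedures". The analysis is descriptive, and the text does not say that events are tabulated by arm.

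Section 14.2, item 10, gives the method of elicitation: one open question on whether anything has got worse since the previous visit, followed by questions on timing, severity, functional impact and relatedness. The team adjudicates the events weekly.

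Section 8.1 says "Increased suicidality is possible during study participation", in a paragraph on the risks of the PTSD diagnosis whether or not the person is treated. For WET it says "Temporary increases in psychological distress can occur among individuals engaged in WET for PTSD".

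The Section 7.3 table schedules the DSI-SS, PHQ-9, GAD-7 and PCL-5 in all seven columns. Section 14.2 places the in-treatment readings before each session. The safeguards text gives their safety purpose: participants "complete self-report questionnaires to monitor PTSD, depression, and suicidality symptoms". That purpose is management of the individual. No section defines worsening on the DSI-SS or plans a comparison of it between arms.

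**The concern.** The protocol names a risk, schedules an instrument for it at every assessment, and then leaves that instrument out of the safety analysis. Entry to the adverse event log depends, as far as the documents show, on what a participant reports in answer to one open question. A participant whose DSI-SS rises but who does not mention it may not appear in the safety summary, although the score is in the database.

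Attribution makes this matter more. Suicidality is a background risk of PTSD, so a single case is hard to attribute to stimulation and could readily be adjudicated as unrelated. Hypothesis 1 looks at the number of events and at how well study-related ones are tolerated. A comparison of arms on a measure taken the same way in everyone is what can separate an effect of stimulation from the background. At stake is how far this pilot's safety conclusion can be carried into the larger trial that it is meant to prepare.

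**Working it through.** **The plan's own figures.** Section 7.4.1 reproduces: 50 × 0.80 = 40 randomised; 40 × 0.15 = 6 dropouts; 40 − 6 = 34 completers. The plan states no power and no precision for safety. Allocation is not stated. I assume 1:1, so 20 per arm, or 17 completers per arm if dropout is equal.

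**Risk, measure and use side by side.**

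| Item | Suicidality | PTSD symptoms |
|---|---|---|
| Named as a risk (8.1) | Yes | Distress, under WET |
| Scale at all seven assessments (7.3) | DSI-SS | PCL-5 |
| Used to monitor individuals (8.1) | Yes | Yes |
| Named by-arm analysis (7.4.3) | None | Mean at each time point (Aim 3) |
| Named in the Aim 1 analysis | No | No |

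The gap is therefore widest for suicidality.

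**Readings that can show a change after stimulation.** There are 7 × 40 = 280 readings in total. Baseline and session 1 come before the first stimulation: 2 × 40 = 80. That leaves 5 × 40 = 200 at most. If the six dropouts contribute none and every completer gives all five, it is 5 × 34 = 170.

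**Precision of a by-arm count** (exact 95% limits; for zero events the upper limit is 1 − 0.025^(1/n)).

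- 0/20: 1 − 0.025^(1/20) = 16.8%.
- 0/17: 1 − 0.025^(1/17) = 19.5%.
- 2/20: 1.2% to 31.7%.
- 4/20: 5.7% to 43.7%.

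For assumed rates of 10% and 30%, the half-width of the 95% interval for the difference is 1.96 × √(0.1 × 0.9/20 + 0.3 × 0.7/20) = 1.96 × 0.1225 = 24 percentage points. Fisher's exact test would have power 0.24 at 20 per arm and 0.19 at 17. A test would serve no purpose; a description with limits would.

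**Would a matching PCL-5 row work?** Section 14.2, item 5, uses one-week recall during treatment and two-week recall otherwise. Like-for-like references are therefore session 1 for sessions 2 to 5, and baseline for one month. Suppose there is no true change, the readings are exchangeable without ties, and the two comparisons are independent. Session 1 is then the highest of its five readings with probability 1/5, and one month does not exceed baseline with probability 1/2. The share flagged by noise alone is 1 − (1/5)(1/2) = 90%. Such a row would carry almost no information.

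**The same check on the DSI-SS rule.** With seven exchangeable readings, the highest falls among the last five with probability 5/7 = 71% if there are no ties. That is a ceiling. The DSI-SS has four items scored 0 to 3 (range 0 to 12), and a participant whose score never moves, for example at zero throughout, cannot be flagged. The documents do not say how common ties will be, so the size of each rise must be shown beside the count.

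**The case against.** The strongest reply is that safety surveillance is wider than the log. A tDCS Reactions form is completed after every session, adverse events are adjudicated weekly, and any indication of suicidal thinking is handled under Consortium procedures. The adverse event SOP is not part of these documents, so a flagged DSI-SS may well be logged. All of this stands. A reader might infer that scale-detected worsening never reaches the safety comparison; the documents do not show that. They show only that no score-based trigger is stated and that neither the Reactions form nor the DSI-SS is named in the Aim 1 analysis.

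A second reply is that symptom worsening is already compared. Section 7.4.3 models the PCL-5 by arm and time, including the in-treatment readings, with simple effects at each time point. A general worsening on active tDCS would show there, so the wider claim that symptom worsening goes unexamined fails. The mixed models are also described for continuous outcomes in general, which could be read to include the DSI-SS. But the scale is not named, and a comparison of means under Aim 3 would not count the participants who got worse.

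Third, Section 8.1 does not present suicidality as a risk of tDCS, and it lists distress under WET, which both arms receive. Both are true. It would be wrong to say that the protocol identifies suicidality as the hazard specific to the combination. For a background risk, though, the sham arm is the reference that is needed.

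Finally, this is an unpowered pilot with descriptive safety. That limits what the added summary can show. It is not a reason to leave scheduled suicidality scores out of a descriptive safety table.

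**Conclusion.** The point holds for suicidality. Aim 1 is a comparison of tDCS with sham, its named outcome and analysis are adverse events only, and an instrument given seven times for a risk that the protocol names has no planned by-arm summary. An unvolunteered rise may therefore be missing from the safety conclusion.

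It is tempting to put the size at 280 unused readings per scale. Only five of the seven readings follow the first stimulation, so for the DSI-SS the figure is at most 200, before dropout. PCL-5 readings are not unused, because they enter Aim 3.

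The conclusion rests on the text as it stands, without sight of the adverse event SOP. The precision figures assume 1:1 allocation, and the 10% and 30% rates are illustrative. The effect on the plan is modest: it improves what Aim 1 can report and leaves the sample size and design unchanged.

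**What to change.** In Sections 7.4.2 and 7.4.3, add a descriptive by-arm DSI-SS summary to Aim 1, specified before unblinding:

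- Among participants with at least one DSI-SS after the first session of tDCS or sham, give the number and proportion whose highest such score exceeds the higher of their baseline and session 1 scores, with exact 95% limits.
- Show by arm the distribution of each participant's largest increase, so that one-point movements can be told from large ones.
- Show by arm the number of post-stimulation readings, because participants who leave early have fewer chances to be counted.
- Report session 2 separately. With weekly sessions, its two-week recall reaches back before the first stimulation.

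Do not add a row for any rise on the PCL-5; noise would fill it in both arms.

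The cost is a small addition to the safety table, from data already scheduled. No participants, visits or instruments are added, and no clinical action changes. The downside is low precision and some natural fluctuation in both arms, so the summary should be read against sham, without a test.
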